3. STUDY DESIGN AND RATIONALE

This Clinical Study Protocol (CSP) has been subject to a peer review according to AstraZeneca standard procedures.

3.1 Overall study design and flow chart

This is a phase I, open-label, two parts (Part A and Part B) study to determine the pharmacokinetics of AZD9291 administered orally at two dose levels (40 mg and 80 mg) in patients with locally advanced or metastatic NSCLC who have progressed following prior therapy with an approved EGFR TKI agent (+/- additional chemotherapy regimens).

Approximately 24 patients will enter into this study, with 12 patients at each dose level

- Cohort 1 will investigate the pharmacokinetics of single then multiple dosing of AZD9291 at 40 mg once daily dose.
- Cohort 2 will investigate the pharmacokinetics of single then multiple dosing of AZD9291 at 80 mg once daily dose.

The enrollment of Cohort 2 will start after Cohort 1 finishes the enrollment. The first 12 patients enrolled in the study will be in 40 mg dose Cohort.

Patients will be administered a single dose of AZD9291 on Day 1, Cycle 0 at the beginning of Part A period. From Day 2 to Day 6, no treatment will be given, but PK samples will be obtained; on Day 8 (Cycle1, Day1), the patients will be administered AZD9291 once daily on a continuous schedule, ie, no break in AZD9291 dosing. Part A will complete after Cycle 4 treatment and Part B will start without treatment interruption.

Patients in both cohorts should continue on treatment with AZD9291 until a treatment discontinuation criterion is met. There is no maximum duration of treatment as patients may continue to receive AZD9291 beyond RECIST 1.1 defined progression as long as they are continuing to receive clinical benefit, as judged by the investigator.

The whole study will be divided nominally into two parts: Part A will assess the pharmacokinetics and preliminary efficacy and safety of AZD9291 at 40 mg and 80 mg respectively, and Part B will assess only the safety and efficacy data of AZD9291.

Following completion of the Part A, patients will automatically continue to Part B.

There are two data cut offs:

- 1. PK and preliminary efficacy and safety data base lock will take place approximately 3 months after LSI and after the part A completes, to allow all patients have two tumor assessments after the first dose.
- 2. Safety and efficacy data base cut off will take place at the earlier time point when either all patients have discontinued treatment and completed 28 days post treatment safety follow-up, or 12 months after the last patient enrolled started investigational product. Data analysis will be performed and a Clinical Study Report (CSR) written based on this data set. Any patients still receiving investigational product at the time of this data cut-off will be able to continue to receive AZD9291 while deriving clinical benefit. Such patients will continue to be monitored for all Serious Adverse Events up to 28 days after the last dose of investigational product. Drug Accountability information must still be collected until all patients have completed treatment.

A CSR will be issued after PK and preliminary efficacy and safety data base lock; a CSR addendum will be issued for updated safety and efficacy information after final safety and efficacy data base lock.

Figure 1 Study flow chart

3.2 Rationale for study design

This study is nominally divided into two parts (Part A and Part B), and is a phase I, open label study to determine the pharmacokinetics of AZD9291 and its metabolites (AZ5104 and AZ7550) in Chinese patients with locally advanced or metastatic NSCLC who have progressed following prior therapy with an EGFR TKI agent. Other additional lines of prior treatment may also have been administered. The primary objective for this study is the characterisation of pharmacokinectics of AZD9291 in Chinese patients following two dose levels of 40 mg and 80 mg once daily respectively.

The majority of patients with EGFRm+ NSCLC respond well initially to treatment with EGFR- TKIs with an ORR of approximately 60 to 70%, but eventually vast majority of the EGFRm+ NSCLC patients develop resistance to EGFR-TKI with a median time to progression of around 9-11 months, due to the emergence of a secondary EGFR mutation. T790M mutation in exon 20 of the EGFR gene represents over 50% of those secondary mutations. Currently, there are no effective standard of care therapies for these NSCLC patients with acquired EGFR-TKI resistance who are T790M+. This patient population with a major unmet medical need, and is therefore, appropriate to be enrolled into the current study for the evaluation of PK, safety/tolerability and early efficacy of AZD 9291.

The doses of 40 mg and 80 mg once daily were selected for PK and safety evaluation based on the recommendation of study D5160C00001, which evaluated PK, safety, tolerability, and efficacy data in patients, living outside China, with locally advanced or metastatic NSCLC who have progressed following prior therapy with a prior EGFR-TKI agent. At the Investigator Brochure (IB) data cut-off of 19 November 2013, AZD9291 had been administered across the dose range of 20 to 240 mg once daily in this study: 20 mg (n=21), 40 mg (n=55), 80 mg (n=47), 160 mg (n=40) and 240 mg (n=7). No dose limiting toxicities (DLTs) have been reported at any dose level in the escalation cohorts during the 21-day DLT evaluation period. Patients have once daily doses of AZD9291 for durations of up to at least 10 months depending on the dose level. Emerging efficacy data has demonstrated durable objective responses from the starting dose level of 20 mg once daily (Ranson, WCLC 2013). The selected 80 mg dose is four fold higher than the minimum efficacious dose tested in study D5160C00001, whilst still being one third of the maximum dose level investigated (240 mg). The 80 mg dose level is considered to have a safety and tolerability profile appropriate for chronic administration to patients with advanced NSCLC and selected to be used in phase II/III trials.

In this study, two dose levels 40 mg and 80 mg once daily will be investigated in Chinese patients for the full pharmacokinetic profile, tolerability and safety. The cohort of 80 mg will start after the enrollment of cohort 40 mg completes.

4. PATIENT SELECTION AND RESTRICTIONS

Investigators should keep a record ie, patient screening log, of patients who entered pre-study screening.

Each patient must meet all of the inclusion criteria and none of the exclusion criteria for this study at the time of starting study treatment. Under no circumstances can there be exceptions to this rule.

4.1 Inclusion criteria

For inclusion in the study, patients must fulfill all of the following criteria:

- 1. Provision of signed and dated, written informed consent prior to any study specific procedures, sampling and analyses
- 2. Aged at least 18 years
- 3. Histological or cytological confirmation diagnosis of NSCLC
- 4. Locally advanced or metastatic NSCLC, not amenable to curative surgery or radiotherapy

- 5. Radiological documentation of disease progression while on a previous continuous treatment with an approved EGFR-TKI eg, gefitinib, erlotinib, icotinib or afatinib. In addition other lines of therapy may have been given.
 - Documented EGFR mutation (at any time since the initial diagnosis of NSCLC) known to be associated with EGFR TKI sensitivity (including G719X, exon 19 deletion, L858R, L861Q).
- 6. World Health Organisation (WHO) performance status 0-1 with no deterioration over the previous 2 weeks and a minimum life expectancy of 12 weeks
- 7. At least one lesion, not previously irradiated that can be accurately measured at baseline as ≥10 mm in the longest diameter (except lymph nodes which must have short axis ≥15 mm) with computerised tomography (CT) or magnetic resonance imaging (MRI) which is suitable for accurate repeated measurements.
- 8. Females should be using adequate contraceptive measures (see Section 4.3), should not be breast feeding and must have a negative pregnancy test prior to start of dosing if of child-bearing potential or must have evidence of non-child-bearing potential by fulfilling one of the following criteria at screening:
 - Post-menopausal defined as aged more than 50 years and amenorrhoeic for at least 12 months following cessation of all exogenous hormonal treatments
 - Women below 50 years old would be consider postmenopausal if they have been amenorrheic for 12 months or more following cessation of exogenous hormonal treatments and with LH and FSH levels in the post-menopausal range for the institution
 - Documentation of irreversible surgical sterilisation by hysterectomy, bilateral oophorectomy or bilateral salpingectomy but not tubal ligation
- 9. Male patients should be willing to use barrier contraception ie, condoms

4.2 Exclusion criteria

Patients must not enter the study if any of the following exclusion criteria are fulfilled.

- 1. Treatment with any of the following:
 - Treatment with an EGFR TKI (eg, erlotinib, gefitinib, icotinib or afatinib) within 8 days or approximately 5x half-life, whichever is the longer, of the first dose of study treatment. (If sufficient wash-out time has not occurred due to schedule or PK properties, an alternative appropriate wash-out time based on known duration and time to reversibility of drug related adverse events could be agreed upon by AstraZeneca and the Investigator)

- Any investigational agents or other anticancer drugs from a previous treatment regimen or clinical study within 14 days of the first dose of study treatment
- Previous treatment with AZD9291, or a 3rd generation T790M-directed EGFR TKIs (eg, CO-1686)
- Major surgery (excluding placement of vascular access) within 4 weeks of the first dose of study treatment
- Radiotherapy with a limited field of radiation for palliation within 1 week of the first dose of study treatment, with the exception of patients receiving radiation to more than 30% of the bone marrow or with a wide field of radiation which must be completed within 4 weeks of the first dose of study treatment
- Patients currently receiving (or unable to stop use at least 1 week prior to receiving the first dose of AZD9291) medications or herbal supplements known to be potent inhibitors or inducers of CYP3A4 (See Appendix H)
- Treatment with an investigational drug within five half-lives of the compound
- 2. Any unresolved toxicities from prior therapy greater than Common Terminology Criteria for Adverse Events (CTCAE) grade 1 at the time of starting study treatment with the exception of alopecia and grade 2, prior platinum-therapy related neuropathy
- 3. Spinal cord compression or brain metastases unless asymptomatic, stable and not requiring steroids for at least 4 weeks prior to start of study treatment
- 4. Any evidence of severe or uncontrolled systemic diseases, including uncontrolled hypertension and active bleeding diatheses, which in the investigator's opinion makes it undesirable for the patient to participate in the trial or which would jeopardise compliance with the protocol, or active infection including hepatitis B, hepatitis C and human immunodeficiency virus (HIV). Screening for chronic conditions is not required.
- 5. Any of the following cardiac criteria:
 - Mean resting corrected QT interval (QTc) >470 msec obtained from 3 electrocardiograms (ECGs), using the screening clinic ECG machine derived QTc value
 - Any clinically important abnormalities in rhythm, conduction or morphology of resting ECG eg, complete left bundle branch block, third degree heart block, second degree heart block, PR interval >250 msec

- Any factors that increase the risk of QTc prolongation or risk of arrhythmic events such as heart failure, hypokalaemia, congenital long QT syndrome, family history of long QT syndrome or unexplained sudden death under 40 years of age in first degree relatives or any concomitant medication known to prolong the QT interval
- 6. Past medical history of interstitial lung disease, drug-induced interstitial lung disease, radiation pneumonitis which required steroid treatment, or any evidence of clinically active interstitial lung disease
- 7. Inadequate bone marrow reserve or organs function as demonstrated by any of the following laboratory values:
 - Absolute neutrophil count $<1.5 \times 10^9/L$
 - Platelet count $<100 \times 10^9/L$
 - Haemoglobin <90 g/L
 - Alanine aminotransferase >2.5 times the upper limit of normal (ULN) if no demonstrable liver metastases or >5 times ULN in the presence of liver metastases
 - Aspartate aminotransferase >2.5 times ULN if no demonstrable liver metastases or >5 times ULN in the presence of liver metastases
 - Total bilirubin >1.5 times ULN if no liver metastases or >3 times ULN in the presence of documented Gilbert's Syndrome (unconjugated hyperbilirubinaemia) or liver metastases
 - Creatinine >1.5 times ULN concurrent with creatinine clearance <50 ml/min (measured or calculated by Cockcroft and Gault equation); confirmation of creatinine clearance is only required when creatinine is >1.5 times ULN
- 8. Refractory nausea and vomiting, chronic gastrointestinal diseases, inability to swallow the formulated product or previous significant bowel resection that would preclude adequate absorption of AZD9291
- 9. History of hypersensitivity to active or inactive excipients of AZD9291 or drugs with a similar chemical structure or class to AZD9291
- 10. Women who are breast feeding
- 11. Involvement in the planning and conduct of the study (applies to AstraZeneca staff or staff at the study site)

12. Judgment by the investigator that the patient should not participate in the study if the patient is unlikely to comply with study procedures, restrictions and requirements

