Corticosteroids and/or bisphosphonates	Patients may receive treatment with corticosteroids and/or bisphosphonates for the treatment of bone metastases.
Palliative radiation	Patients may receive radiotherapy for painful bony metastases.
Supportive care and other medications that are considered necessary for the patient's well-being	To be administered as directed by the investigator.

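### Exclusion 1 turns an evident 4-week washout after wide-field or extensive-marrow radiation into a 4-week maximum with no minimum

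*Protocol*

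**What the plan says.** Section 4.2 of the protocol lists treatments that bar entry. Its radiotherapy bullet has two parts. The first is an ordinary look-back exclusion: "Radiotherapy with a limited field of radiation for palliation within 1 week of the first dose of study treatment". The second excepts patients whose irradiated volume takes in over 30% of the marrow, and likewise those treated "with a wide field of radiation which must be completed within 4 weeks of the first dose of study treatment".

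Two other bullets under the same number show how the list normally expresses a washout: "Major surgery (excluding placement of vascular access) within 4 weeks of the first dose of study treatment" and "other anticancer drugs from a previous treatment regimen or clinical study within 14 days of the first dose". In both, the stated period is the time in which the treatment is forbidden.

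Section 4 adds that the criteria must be met when study treatment starts and that no exceptions are allowed. Section 5.5.2 repeats this.

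**The concern.** In the second part of the radiotherapy bullet, the verb changes the meaning. The other bullets name a treatment and a barred period. This clause says the radiation has to be completed inside the period, so the window becomes a condition to satisfy. Because the clause is an exception to the 1-week rule, it also lifts that rule for the same patients. The larger radiation exposure is left with a weaker time rule than the smaller one.

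What is at stake is patient safety at entry, chiefly marrow recovery, and consistent eligibility decisions. Two sites could decide opposite ways on the same patient, one following the words and the other the presumed intent, in cohorts of about 12. No effect on an event rate or on the PK results is claimed.

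**Working it through.** No sample size, error rate or event count is involved. The check sets the clause beside its neighbours and looks for text elsewhere that corrects it.

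**Inputs (protocol Section 4.2, exclusion 1).** Limited-field window: 1 week = 7 days. Figure for wide-field or >30%-marrow radiation: 4 weeks = 28 days. Major surgery: 4 weeks barred. Other anticancer drugs: 14 days barred.

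**Literal reading.** Let g be the days from the end of wide-field or >30%-marrow radiation to first dose.

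| | Rule on g | g = 1 day | g = 56 days (8 weeks) |
|---|---|---|---|
| As written | 0 ≤ g ≤ 28 | admitted | not admitted |
| Evident intent | g ≥ 28 | excluded | admitted |

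The two rules share at most the boundary value g = 28. The minimum gap as written is 0 days, against 7 days for limited-field palliation.

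**Why a minimum was meant.**
- The clause stands in a list of reasons not to enroll.
- The surgery and drug bullets use the same phrasing for a barred period.
- Heavier radiation is taken out of a 1-week rule and given a 4-week figure, which makes sense only as a longer washout.
- The literal rule has no plausible purpose: it favors patients with the least recovery time.

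**Does other text supply the washout?**
- The 14-day bullet covers investigational agents and anticancer drugs, not radiation.
- Inclusion 7 ("At least one lesion, not previously irradiated that can be accurately measured at baseline") concerns which lesion can be measured, not when radiation ended.
- Section 4.3.1 ("Patients may receive radiotherapy for painful bony metastases") governs treatment during the study.

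None sets an interval before first dose.

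**What limits the harm.**
- Exclusion 2 bars "Any unresolved toxicities from prior therapy greater than Common Terminology Criteria for Adverse Events (CTCAE) grade 1 at the time of starting study treatment", with exceptions for alopecia and grade 2 neuropathy from platinum therapy.
- Exclusion 6 covers a history of "radiation pneumonitis which required steroid treatment, or any evidence of clinically active interstitial lung disease".
- Exclusion 7 sets limits for neutrophils, platelets and hemoglobin.
- Section 6.3.5 requires haematology at screening and before the first dose (no repeat if screening was within 7 days), then before dosing on Cycle 1 Days 1, 8 and 15.

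Daily dosing starts about 7 days after the single dose. With the zero-day visit window in Table 2, the Cycle 1 samples fall 7, 7 + 7 = 14 and 7 + 14 = 21 days after first dose. With the 7 ± 2 day gap in Section 5.4.2, they fall at 5–9, 12–16 and 19–23 days. The difference does not affect the point.

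**The case against.** The strongest reply is that the clause is clumsy but will not be misapplied. It sits under a heading that says who must not enter, its neighbors use the same phrase for a forbidden period, and an investigator would reach the 4-week washout from context. The literal upper limit is also the weaker half of the reading. The exception speaks of patients receiving radiation, so it may not reach someone irradiated months ago, and turning that patient away while accepting one irradiated yesterday is a result no investigator would want. Finally, exclusions 2, 6 and 7 apply when treatment starts and would stop a patient with unrecovered marrow or lung toxicity whatever the interval.

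Much of this stands. Many sites probably will infer the intent, the 28-day ceiling is one construction of loose wording, and the entry checks keep the practical effect small. The missing minimum remains. To find one, the reader must take a requirement to complete radiation inside a window as a prohibition on radiation in that window. The criteria allow no exceptions, and this bullet, unlike the EGFR TKI bullet, gives no room to agree another washout. Blood counts and toxicity grades show the patient's state at one time and do not replace a set interval.

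**Conclusion.** The clause is wrong as written. It sets no minimum interval after wide-field or >30%-marrow radiation (0 days, against 7 days for limited-field palliation) and literally imposes a 28-day maximum where a 28-day minimum was evidently meant.

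Severity is minor. The other entry criteria and the early laboratory schedule limit the safety consequence, and the primary objective, sample size and analysis do not change. The conclusion that a 4-week washout was intended is an inference from the structure of the list, though a strong one. The number of patients affected cannot be estimated, because the protocol gives no figure for prior radiation of this kind.

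**What to change.** Replace the bullet with two exclusions of the same form as the others in the list:

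- "Radiotherapy with a limited field of radiation for palliation within 1 week of the first dose of study treatment"
- *Wide-field radiation, or radiation to over 30% of the bone marrow, ending less than 4 weeks before the first study dose.*

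The cost is one amended bullet. Any patient enrolled under the literal reading soon after such radiation would have to start later. At sites that already apply a 4-week washout, nothing changes.

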4.3 Restrictions

The following restrictions apply while the patient is receiving study treatment and for the specified times before and after:

- Females of child-bearing potential should use reliable methods of contraception from the time of screening until 3 months after discontinuing study treatment. Acceptable methods of contraception include total sexual abstinence, tubal ligation, hormonal contraceptives that are not prone to drug-drug interactions (IUS Levonorgestrel Intra Uterine System (Mirena), Medroxyprogesterone injections (Depo-Provera), copper- banded intra-uterine devices and vasectomised partner. All hormonal methods of contraception should be used in combination with the use of a condom by their male sexual partner for intercourse.
- 2. Male patients should be asked to use barrier contraceptives (ie, by use of condoms) during sex with all partners during the trial and for a washout period of 3 months. Patients should avoid procreation for 6 months after completion of trial treatment. Patients should refrain from donating sperm from the start of dosing until 6 months after discontinuing study treatment. If male patients wish to father children they should be advised to arrange for freezing of sperm samples prior to the start of study treatment.
- 3. Once enrolled all patients must try to avoid concomitant use of medications, herbal supplements and/or ingestion of foods with known potent inducers of CYP3A4 whenever feasible, but patients may receive any medication that is clinically indicated for treatment of adverse events. Such drugs must have been discontinued for an appropriate period before they enter screening and for a period of 3 months after the last dose of AZD9291. All concomitant medications should be captured on the eCRF. Guidance on medicines to avoid, medications that require close monitoring and on washout periods is provided (see Appendix H).
- 4. Patients who wear contact lenses must discontinue wearing their lenses if they have any mild to moderate eye symptoms (CTCAE grade ≤2) while receiving treatment with AZD9291 until at least one week after symptoms have resolved. If a patient has a recurrence of eye symptoms or experiences any severe (CTCAE grade ≥3) ocular events they must discontinue wearing their contact lenses until at least one week after treatment with AZD9291 is permanently discontinued. Patients must not use any eye drops or ointment for treatment of eye symptoms, unless agreed by a study doctor, at any time during the study until 1 week after AZD9291 has been permanently discontinued. Patient should consult the clinic promptly if they have any concerns.

For restrictions relating to concomitant medications see next Section 4.3.1.

